## 5.1

Cognitive Assessment: Participants will complete a 30-35min battery of cognitive tests that are correlated with dual tasking, functional capacity, and/or falls. We will minimize the potential for procedural learning within this battery by having participants complete the battery as "practice" at the end of the in-person screen. Moreover, tests were selected that have alternate forms, or, were felt to be resistant to practice effects. All tests have excellent psychometric properties and normative data covering the range of demographic characteristics of our proposed sample, with minimal ceiling and floor effects. Tests will include the Trail Making Test (A and B) of executive function (i.e., speeded visual search, vigilance and set-shifting). For this primary outcome, we will utilize the original Test B at baseline, and three alternative forms of Part B, which have comparable psychometric properties, for each of the three follow-ups. Participants will also complete the MoCA test of global cognitive function, WAIS-IV Digit Span (Forwards, Backwards) test of working memory, the WAIS-IV Coding test of sustained attention and motor speed, the Category and Phonemic Fluency tests of semantic knowledge and word retrieval, and the Hopkins Verbal Learning Test – Revised (HVLT-R) of verbal episodic memory. Staff will be trained in all assessment procedures by our co-investigator, [name] (with ongoing supervision to ensure standard administration and scoring).

Mood will be assessed as it influences performance on clinical tests of physical and cognitive function, and long-term exposure to tDCS may affect (i.e., improve) mood. We will use the Center of Epidemiology Studies-Depression Scale Revised (CESD-R) scale, which has been used extensively in epidemiology studies and consists of 20 questions regarding feelings of depression, worthlessness, loneliness, energy level, and fear. The CESD-R has high internal consistency ( $r=0.90$ ) and a test-retest reliability of 0.51.

Pain: Similar to mood, lower-extremity pain is common in older adults with previous falls, interferes with function and may benefit from tDCS. Participants will complete the Brief Pain Inventory, which quantifies pain location, pain intensity and the extent to which pain interferes with daily functioning.

Falls tracking: As the recruited cohort will have high risk of falling and related injuries during follow-up may influence physical and cognitive performance, falls will be tracked using monthly falls calendars. Participants will be asked to mark the fall on the calendar and complete a form every time they fall. Staff will review calendars at each monthly follow-up visit, to discuss the incidence and characteristics of falls. Falls tracking will also provide preliminary data on falls rates by group, to be used for planning of future studies.

[figure not shown]
Habitual physical activity will be recorded for five consecutive days at baseline and the immediate, three- and six-month follow-ups using a lightweight water-proof sensor taped to participant's low-back (L5 vertebral level) (Axivity Inc., United Kingdom). This device has been

validated for use in older adults of various function level. It provides overall activity and step counts, as well as accurate, automatic detection of time spent lying, sitting, standing and walking and gait kinematics during detected bouts of walking.

**Visits 4-23—(Up to 40 minutes) tDCS Intervention** at the Clinical Research Laboratory at Hebrew Rehabilitation Center, Roslindale, MA :

Trained research assistants will administer the tDCS intervention to the participant over twenty visits that will be completed Mon-Fri over four consecutive weeks at approximately the same time of day.

**tDCS interventions:** Participants will be randomized to receive tDCS that facilitates the excitability of their left dlPFC, or sham stimulation (Figure 5). The left dlPFC was chosen because it is part of the frontoparietal control network, a key contributor to executive function and the processing of sensory feedback for the control of actions, and it is activated when standing or walking—especially when dual tasking. tDCS targeting this region has been studied extensively: it appears to mitigate dual task costs to standing and walking in older adults (See Preliminary Studies) and enhances numerous aspects of cognitive-motor function when tested over shorter follow-up periods. It has also shown efficacy for depression and chronic pain.

**Figure 5: tDCS intervention:** The left dlPFC target depicted on a standard brain (red). The 'Stimweaver' algorithm (Section 3.2) optimizes tDCS by providing electrode placement and current parameters that maximize the electric field's normal component ( $E_n$  V/m) into the target, with minimal impact elsewhere. Warmer/cooler colors reflect greater positive/negative  $E_n$ . Positive electrodes=red; negative=blue. In this trial, each intervention will be personalized by using participant MRIs within this algorithm.

Personalized tDCS: Electrode placement and current parameters will be optimized to each participant by importing their MRI into *Stimweaver*, with the goal of generating an average electric field of 0.25 V/m^77 within their identified left dlPFC. The direct current delivered by any one electrode will not exceed 2.0 mA; the total amount of current from all electrodes will not exceed 4 mA. Each 20-minute session will begin and end with a 60-second ramp up/down of current amplitude to maximize comfort.

Personalized Sham: We will use an active sham in which very low-level currents (0.5 mA total) will be transferred between electrodes in close proximity on the scalp throughout the entire 20-minute session. This intervention will be optimized to each participant to deliver currents designed to not significantly influence their cortical tissue, but still mimic the cutaneous sensations induced by tDCS. We have shown that this active sham effectively blinds participants to stimulation condition and does not effect functional outcomes.

Intervention characteristics: Each intervention will comprise 20, 20-minute sessions of stimulation completed over four consecutive weeks. Our pilot RCT demonstrated significant effects of 10 tDCS sessions over two weeks in a similar population of older adults over a shorter follow-up period. At the same time, several well-designed trials have recently reported lasting benefits of multi-session tDCS interventions on depression, pain, stroke, and Parkinson's disease, which have each tested interventions ranging from 8-20 sessions. We therefore believe 20 sessions constitutes a safe and feasible intervention, and that it will maximize the duration of expected effects, yet not over-burden participants with study visits. tDCS sessions will be administered at approximately the same time of day. Participants will continue taking their medications throughout the intervention, and will be asked to inform the study team of a change in medication usage.

Double-blinding and safety procedures: tDCS will be delivered by personnel certified in tDCS administration by the Berenson-Allen Center for Noninvasive Brain Stimulation at the BIDMC, which is directed by our co-investigator, [name]. Similar to our most recent studies, tDCS will be delivered using the Startstim-8™ device and software (Neuroelectrics Corp, Cambridge MA), which enables custom amounts of current to be delivered through an array of eight Pi™ gel Ag/AgCl electrodes placed on the scalp according to the 10-20 EEG convention. Study personnel administering tDCS and the participants will not be aware of tDCS intervention arm assignment. We will ensure such double-blinding by programming the tDCS software with intervention-specific stimulation codes, as supplied by personnel uninvolved in data collection, prior to study initiation. At the end of each visit, subjects will complete a questionnaire to report potential side effects (e.g., skin irritation, headache, etc). In accordance with recent recommendations, the efficacy of tDCS blinding will also be assessed by asking each participant—and study team member administering tDCS—to judge whether real or sham tDCS was given, as well as their certainty of this judgment. This questionnaire will be completed at the end of the first tDCS session, at the end of the last tDCS session and at the final follow-up assessment.

**Visits 24-26—(Up to 2.5 hours each visit)Follow-up Assessments at the Clinical Research Laboratory at Hebrew Rehabilitation Center, Roslindale, MA :** Participants will repeat the baseline assessment immediately post-intervention - Visit 24 (within 3 days following the final tDCS visit) and again at three-Visit 25, and six months - Visit 26. Trained research assistants will administer all the follow-up assessments at visits 24-26.

---

**List any additional source(s) of data to be used in the study**

*e.g., hospital records, clinical and office charts, checklists, pharmacy dispensing records, etc.*

None

#### **Are any procedures being performed as routine medical care?**

5.3

*e.g. for diagnostic or treatment purposes, etc.*

Yes

No

#### **List procedures being performed solely for the research**

5.4

All procedures within the protocol will be performed solely for research purposes.

#### **Describe the methods used to protect participant privacy**

The following are the planned procedures for effectively protecting against and minimizing loss of participant privacy:

5.5

1. Phone screenings will be conducted in a private office space.
2. Study visits will be conducted in private rooms located within laboratory.
3. Each participant will be given a unique study identification number and data will not include any of the participant's PHI.
4. All participant-identifying information will be stored and managed on a secured database server. The information will be password protected.
5. Participant confidentiality will be maintained in accordance with HIPAA regulations.
6. Only the PI and study personnel approved by the IRB and authorized to view PHI will have access to the information.
7. PHI will not be used during discussion, presentation or publication of any research data.
8. Files containing PHI data collected for recruitment and screening purposes will be kept in locked, secured filing cabinets accessible only to designated study personnel (research assistants and investigators).

5.6

#### **Are there data collection instruments or assessments to be used in the study?**

Yes

#### **List all of the data collection instruments and assessments**

*Note: If any materials are not yet available, please indicate that information in this section.*

Assessment of Protocol Understanding  
Height and Weight Form

Timed Up and Go (TUG) Form  
Falls Questionnaire  
Falls Efficacy Scale - I Questionnaire  
tDCS Blinding Efficacy Questionnaire  
tDCS Side Effects Questionnaire  
Short Physical Performance Battery (SPPB) form  
Neuropsychology Cognitive Testing - Trail Making Task (TMT); Montreal Cognitive Assessment (MoCA); Wechsler Adult Intelligence Scale (WAIS IV) - digit span (forwards/backwards), Coding test, and Category/Phonemic Fluency; Hopkins Verbal Learning Test - Revised (HVLT-R)  
Medical History Questionnaire  
Medication Review Form  
Clinical Dementia Rating (CDR) Form  
Suicide Risk Protocol  
Brief Pain Inventory  
Dual Task (DT) Gait and Balance Forms  
Dual Task Familiarization and Sitting Form  
Blood Pressure Form  
Center for Epidemiology Studies Depression Scale Revised (CESD-R)  
Socio-demographics Form  
Personalized tDCS Phone Screen Questionnaire  
Personalized tDCS eligibility Questionnaire  
MRI Safety Screening Form

**Attach all instruments and assessments to be used in the study**

---

[Assessment of Protocol Understanding Form.docx](#)  
[Height and Weight Form v171318.docx](#)  
[TUG form\\_1 71318.doc](#)  
[Falls Questionnaire\\_v107132018.docx](#)  
[Falls Efficacy Scale\\_I.pdf](#)  
[tDCS Blinding Efficacy Questionnaire.docx](#)  
[tDCS Side Effects Questionnaire.docx](#)  
[SPPB Form\\_1 7132018.doc](#)  
[Neuropsych testing response sheets.pdf](#)  
[Medical History Questionnaire\\_1 71318.docx](#)  
[Medication Review Form\\_1 71318.docx](#)  
[TIC.pdf](#)  
[MoCA-Test-English\\_v\\_1.pdf](#)  
[CDR.NACCb4\\_tfp.pdf](#)  
[Suicide Risk Assessment Protocol.pdf](#)  
[Brief pain inventory\\_long form v1 71318.docx](#)  
[DT gait assessment\\_1 71318.docx](#)  
[Dual Task Balance Assessment\\_1 71318.docx](#)  
[Dual Task Familiarization and Sitting Assessment\\_v1 07132018.docx](#)  
[Blood Pressure Form\\_v2.docx](#)  
[CESD\\_R.1 71318.docx](#)  
[Sociodemographic Form.docx](#)

[Personalized tDCS Eligibility Questionnaire\\_clean.docx](#)

[Personalized tDCS in Fallers\\_PhoneScreenQuestionnaire\\_v1\\_071218 IRB edits Clean version.docx](#)

[MRI RSH Safety Form ver 15\\_Jul2018 protected.pdf](#)

No

## 6.0 Statistical Plan

---

### Statistical Methods

---

#### Overall approach:

Exploratory analyses will be used to assess outcomes distributions, and any necessary transformations (e.g. to combat significant skew) will be performed prior to estimation of mean treatment effects. Said estimation will use **mixed effects linear regression** of post-intervention outcomes immediately following intervention and at three and six months, with random intercepts and slopes to account for serial correlation in repeated measurements on individuals; models will control for baseline outcomes as in analysis of covariance. Owing to the potential for nonlinear trends in outcomes with time, we will assume no functional form of temporal trends. Missing data will be accommodated by multiple (at least 50) imputation of missing records using algorithms to accommodate the clustered nature of the longitudinal design. Analyses will adjust for the stratified design effect (i.e. control for sex). All estimates will be accompanied by 95% confidence intervals (CIs) for the purposes of reporting in publication. Limited hypothesis testing will be performed at the 0.05 level, but emphasis will be on estimation. Owing to the focused nature of the design and prespecification of hypotheses, no interim analyses are planned, and no significance 'adjustment' will be applied for multiplicity.

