**Aim-specific Analytic Plan and Power:** **Aim 1** will test the effect of tDCS on dual task costs to standing and walking. The mixed-effects regression approach described above will estimate mean differences between tDCS and sham outcomes at the end of intervention and at three and six months thereafter. We will test the hypothesis that post-intervention changes in outcomes differ between randomized arms, and will additionally estimate timepoint-specific differences between arms in order to assess duration of effects. These models will control for dual-task cost to serial subtraction performance (as a time-varying covariate) to isolate the costs to gait by adjusting for potential differences in task prioritization over time. Sensitivity assessments will stratify by sex to assess empirical evidence of sex-specific effects (see below). Association between model-based estimates of subject-specific intercepts and slopes (generated as random effects) will be examined to assess the degree to which change with time is associated with the average level of function denoted by each measurement. **Sample size estimates:** Prior experiences suggest that 1) inter-individual standard deviation of dual-task costs under either sham or intervention will be no greater than 20%, 2) serial measures of dual task costs express substantial within-participant correlation, in excess of 0.8, and 3) real tDCS intervention reduces dual task costs (Section 3.3.2.2). We assume conservatively that the proposed study will obtain serial correlation of at least 0.75. Assuming evaluable data on at least 57 participants per arm, the trial will provide **90% power to detect a mean difference of 8% between intervention and control arms** in a comparison of dual task costs at any time following cessation of intervention.

The trial will thus be well-powered to detect differences more subtle than the clinically-meaningful differences observed between those with and without a history of falls.  
43-50

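### Random intercepts and slopes are the only stated covariance for three post-intervention visits; per-visit standard errors can be off by several per cent, and an unstructured covariance avoids this

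*Combined protocol and SAP*

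**What the plan says.** Section 6.0 (Statistical Methods, Overall approach) specifies a linear mixed model "of post-intervention outcomes immediately following intervention and at three and six months". Correlation between a person's visits is to be handled "with random intercepts and slopes to account for serial correlation in repeated measurements on individuals". Baseline enters as a covariate: "models will control for baseline outcomes as in analysis of covariance". For the time trend, "we will assume no functional form of temporal trends".

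Under Sample size determination, Aim 1 first tests the overall difference between arms, and the plan "will additionally estimate timepoint-specific differences between arms in order to assess duration of effects". Power of 90% for a difference of 8 is claimed "in a comparison of dual task costs at any time following cessation of intervention". The correlation input is a single lower bound: "We assume conservatively that the proposed study will obtain serial correlation of at least 0.75". Aim 1 also uses the random effects as an output: "Association between model-based estimates of subject-specific intercepts and slopes (generated as random effects) will be examined".

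Neither section gives a residual covariance structure, an unstructured alternative, a robust standard error, or a rule for a singular or non-converged fit.

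**The concern.** With baseline as a covariate, the outcome vector has three visits. Their 3x3 within-person covariance has six free elements. A random intercept, a random linear slope, their covariance and one residual variance give four. Each person's deviation from the mean is then linear in time, and the three visit variances are tied together.

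Aim 1 reads duration of effect from arm differences at each visit, and the Overall approach puts the emphasis on estimates with 95% confidence intervals. When visit is categorical, covariate effects vary by visit and the data are complete, the standard error at a visit is determined by the fitted variance at that visit. Misfit there passes into the interval. The error also differs by visit, so it distorts the comparison that is meant to show how long an effect lasts.

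The intercept-slope association has a separate weakness. It means something only if the slope variance is estimated away from zero, and the plan does not say what happens when it is not.

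**Working it through.** **Inputs from the documents.** 57 evaluable per arm, SD 20, correlation 0.75, difference 8, two-sided 0.05 (Aim 1); SPPB SD 1.5, effect 0.5, correlation 0.75, power 92% (Aim 2).

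**Assumed.** Independent, equal-variance residuals in the random-slope model; the true covariance patterns in the table.

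**1. The plan's own figures.** Aim 1, analysis of covariance at one visit: residual SD = 20 x sqrt(1 - 0.75^2) = 13.23; SE = 13.23 x sqrt(2/57) = 2.48; power = 89.8%, against 90% stated. The random-effects covariance plays no part in this calculation.

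Aim 2, mean of three visits given baseline, all correlations 0.75: each conditional variance is 1 - 0.5625 = 0.4375 and each covariance 0.75 - 0.5625 = 0.1875 (in units of SD squared). The variance of the mean is (3 x 0.4375 + 6 x 0.1875)/9 = 0.271. Then SE = 1.5 x sqrt(0.271) x sqrt(2/57) = 0.146 and power = 92.8%, against 92% stated. Correlation decaying as AR(1) gives 74.9%. The Aim 2 figure therefore implies equal correlation across visits, although the text never says so.

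**2. What the model allows.** Let a, b and c be the intercept variance, the intercept-slope covariance and the slope variance, and s the residual variance, with visits at 0, 3 and 6 months.

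- V0 = a + s
- V3 = a + 6b + 9c + s
- V6 = a + 12b + 36c + s

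Hence V3 = (V0 + V6)/2 - 9c. Since c cannot be negative, the 3-month variance cannot exceed the average of the other two. Equal variances at all three visits require b = c = 0, which makes the correlation exchangeable.

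**3. Per-visit standard errors.** Ratio = sqrt(large-sample fitted variance / true variance), 57 per arm. SD patterns are for the immediate, 3- and 6-month visits. Rows that give SDs in units assume correlation 0.75 and condition on a baseline SD of 20.

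| Assumed truth | Immediate | 3 months | 6 months | Type I error at 3 months |
|---|---|---|---|---|
| Equal SDs, equal correlation | 1.00 | 1.00 | 1.00 | 5.0% |
| AR(1) 0.4 to 0.8, equal variances | 1.02-1.03 | 0.945-0.964 | 1.02-1.03 | 5.9-6.4% |
| AR(1) 0.75 including baseline | 1.059 | 0.923 | 1.029 | 7.0% |
| 3-month SD 15% higher | 1.05 | 0.915 | 1.05 | 7.3% |
| SD 18/20/18 | 1.038 | 0.935 | 1.038 | 6.7% |
| SD 16/18/20 | 1.029 | 0.998 | 0.983 | 5.0% |
| SD 16/20/16 | 1.090 | 0.872 | 1.090 | 8.8% |
| SD 14/20/20 | 1.142 | 0.901 | 1.019 | 7.8% |
| SD 20/16/20 | 0.949 | 1.144 | 0.949 | 2.5% |

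For SD 18/20/18 the 3-month SE is reported as 2.32 when it should be 2.48, so the 95% half-width is 1.96 x 2.32 = 4.55 instead of 1.96 x 2.48 = 4.86. A more extreme pattern, 12/20/20, gave an immediate SE 24% too large. The ratio for the visit-averaged contrast is essentially 1.00 throughout.

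Finite-sample simulation (4,000 trials each) gave 3-month type I error, random slopes against unstructured, of 6.5% against 5.0% (AR(1) 0.6) and 7.1% against 4.8% (3-month SD 15% higher).

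**4. Singular fits.** With three equally spaced visits, the slope variance is positive only if the linear contrast varies more than the quadratic one. Under equal variances and equal correlation the two have the same true variance, so which is larger is close to a coin toss. Simulated singular share: 52.7% with 114 people, 52.5% with 144; direct optimiser fits gave 53%. In these fits the per-visit SE ratio averaged 0.996 to 0.998.

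The share depends on equal correlation. If the immediate-to-6-month correlation is 0.72, 0.70 or 0.65 rather than 0.75, it falls to about 23%, 11% or 1% (114 people). Under AR(1) 0.75 it is about 0.2%.

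**The case against.** - **A reader might infer that the plan contradicts itself**, assuming no temporal form while fitting linear slopes. It does not. The statement about form follows a remark on nonlinear trends in outcomes and concerns the mean. A free mean with random slopes is coherent, and the estimated arm differences are not forced onto a line.
- **A reader might infer that the 90% power is wrong.** It comes from a single-visit formula, reproduces at 89.8%, and does not change under the fix.
- **A reader might combine the two problems** and conclude that, under the plan's own assumption, half the fits are singular and the intervals are therefore wrong. Where the one-in-two figure applies, the standard errors are correct; under decaying correlation they are biased but singular fits are rare. The two can coincide when the 3-month variance is raised, because the slope variance is then pushed to zero, but the documents give no such pattern.
- **A constant correlation of 0.75 is not stated.** The text gives a lower bound. Equality across visits is an inference from the Aim 2 figure.
- **The four-parameter count rests on default residuals.** The plan states none, so part of the point is missing specification.
- **The per-visit differences are additional** to the overall test, and hypothesis testing is described as limited. This stands and lowers the weight of the point.
- **The checks are simplified.** They include no missing data, multiple imputation or time-varying covariate, all of which are planned. Imputation adds between-imputation variance to the interval, so the percentages are approximate.

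**Conclusion.** The point holds as an inexpensive improvement to the specification. The visit-averaged treatment effect, the mean trend and the sample size are not in question.

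Under moderate assumed departures, the per-visit standard errors are wrong by roughly 2-9%, typically too small at 3 months (type I error about 6-7%) and too large at the outer visits. In wider patterns the error reaches about 14%, and the direction reverses if the 3-month variance is the low one. A steady rise in SD (16/18/20) costs at most 3%. These sizes rest on covariance patterns chosen for illustration and on independent, equal-variance residuals.

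Under equal variances and correlations, the intervals are sound. The harm is then confined to about one fit in two being singular, with no rule for handling it across at least 50 imputed data sets and four primary outcomes (two dual task costs, SPPB, Trail Making Test). The planned intercept-slope association is degenerate in such fits.

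**What to change.** In the Overall approach, replace the random intercepts and slopes in the primary model with visit as a category, arm-by-visit, baseline outcome-by-visit, sex, and an unstructured 3x3 within-person covariance. The Aim 1 time-varying covariate can stay as planned. Fit by REML in every imputed data set with small-sample degrees of freedom such as Kenward-Roger, and state how these are pooled across imputations. Name a fallback for non-convergence that still gives each visit its own variance, such as heterogeneous Toeplitz.

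In the Aim 1 text, move the intercept-slope association to a separate exploratory random-effects model and say how singular fits will be reported.

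The cost is two more covariance parameters, which 114 to 144 people with three visits can support, a matching edit to Aim 1, and a pooling rule. No new data are needed. Under the plan's own inputs the per-visit SE remains 2.48 and power 89.8%. The change should be made before unblinding, so that the covariance is not chosen after seeing results.
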